18.3 Randomization and Stratification

This will be a single arm phase II study and no randomization or stratifications will be involved

18.4 Evaluation of toxicity.

All patients will be evaluated for toxicity from the time of their first treatment with erlotinib. All of the surgical procedures in the protocol are the usual standard of care in treating patients with stage III NSCLC. However, we will monitor and record all postoperative complications. Certain postoperative complications are expected after lung resection and/or mediastinoscopy. We will particularly monitor 30 day mortality, development of bronchopulmonary fistula or prolonged wound healing. If the rate of these is more than what is expected as standard of care, the regulatory authorities will be reported and the trial will be suspended for toxicity.

18.5 Evaluation of response.

All patients who meet the eligibility criteria and have received at least one dose of treatment will be assessed for response to treatment.

19.0 REFERENCES:

5. Non-small Cell Lung Cancer Collaborative Group. 1995. Chemotherapy in non-small cell lung cancer: a meta-analysis using updated data on individual patients from 52 randomized clinical trials. *Br Med J* 311(7010):899-909.

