4.2 Surgery

Patients who had significant clinical down staging and deemed medically fit to tolerate surgery will have surgical resection within 4-6 weeks after last staging imaging studies. Patients will continue on erlotinib until one day prior to surgical resection.

Patients with non-progressive disease who are not going for surgery should have mediastinal restaging done by either EUS/EBUS or mediastinoscopy.

The patient could receive either adjuvant chemotherapy, radiotherapy or both after surgical resection at the discretion of the treating physician. For the patients with unresectable, non-progressive disease, repeat mediastinal staging is required prior to proceeding with either chemotherapy, radiotherapy or both. Patients are also required to have repeat mediastinal evaluation even if the treating physician decides to continue on erlotinib beyond study duration.

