8.3 Tissue Requirements and Assays

Although high throughput techniques like microarray and proteomics will allow simultaneous determination of up to thousands of genes and proteins in patients before and after the treatment, it is limited by the need for large amounts of tumor tissues and labored collection. Thus, we will focus on several biomarkers suggested by our and others preclinical studies for erlotinib to predict their clinical response and benefit, and only performed array-based genomic analysis and proteomics in selected patients.

8.3.1 Tissue requirements:

Tumor samples: We will put all efforts to obtain at least the diagnostic tissue blocks for the correlative studies. Tumor tissues will be available from the diagnostic biopsy. Pre- and post-treatment tumor biopsies will be obtained in available patients. The tumors will be embedded in OCT solution or snap frozen in a liquid nitrogen bath. Aliquots of tumors will be fixed in formalin and embedded in paraffin.

Skin samples: Serial 3mm-punch skin biopsies under local anesthesia on the back of upper torso are minimal invasive and can be done within 20 minutes during an outpatient visit. This is required only for all patients enrolled in the study who consent to the biopsy, with or without the presence of grade 2 or above skin rash after initiation of erlotinib. A separate or immediate after clinic visit with the treating physician might be arranged to perform the skin biopsy as needed. These samples (~400 mg) will be snapped frozen immediately in liquid nitrogen, and embedded in paraffin.

Timing of tumor or skin biopsy: Pre-treatment biopsy could be obtained within 2 weeks before initiation of the drug treatment. The onset of skin rashes is usually two weeks in patients and last for at least 24 hours after last dose of erlotinib, Thus we will perform post-treatment skin biopsy during the planned surgical resection for lung cancer OR at the peak of skin rash as per patient and treating physician's discretion.

8.3.2 Tissue resources:

The following tissue resources are allowed to collect tissue samples at the time of initial diagnosis, pre- and post-treatment.

- 8.3.2.1 Formalin-fixed, paraffin-embedded (FFPE) tumor blocks
- 8.3.2.2 Endobronchial brush and wash
- 8.3.2.3 CT-guided core biopsy of tumor
- 8.3.2.4 Punch biopsy of skin
- 8.3.2.5 Peripheral blood

8.3.3 The following assays will be performed:

1. Histological Evaluation
2. DNA isolation and mutational analysis

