12.1 Definitions

An adverse event can occur on any clinical trial; it is the responsibility of the Principal Investigator and his/her research team to identify, review and report all necessary adverse events to the institutional IRB, the sponsor and governmental agencies (i.e., NCI and/or FDA) as appropriate. Adverse events should be identified through standard, routine protocol review and clinical assessment of each subject participating in the clinical trial. This review should be timely in order to meet the requirements for adverse event reporting defined below.

An adverse event An Adverse Event (AE) is defined as any untoward medical occurrence in a patient or clinical investigation subject administered a pharmaceutical product and that does not necessarily have to have a causal relationship with this treatment. An AE can therefore be any unfavorable and unintended sign (including an abnormal laboratory finding), symptom, or disease temporally associated with the use of erlotinib whether or not considered related to erlotinib.

During clinical trials, adverse events can be spontaneously reported or elicited during open-ended questioning, examination, or evaluation of a subject. (In order to prevent reporting bias, subjects should not be questioned regarding the specific occurrence of one or more adverse events.)

Adverse events (AEs) will be recorded in the case report form for the duration of the trial, regardless of whether or not the event(s) are considered related to trial medication. All AEs considered related to trial medication will be followed until resolution even if this occurs post-trial.

Adverse events (AEs) will use the descriptions and grading scales found in the revised Common Terminology Criteria for Adverse Events (CTCAE) version 4.0 (Appendix C). A list of adverse events that have occurred or might occur (Reported Adverse Events and Potential Risks) can be found in Section 6 (Pharmaceutical Information). The reported procedures to be followed are presented in the investigators' brochures.

In the context of multicenter clinical trials, Adverse Events can be characterized as either internal adverse events or external adverse events. From the perspective of one particular institution engaged in a multicenter clinical trial, internal adverse events are those adverse events experienced by subjects enrolled by the investigator(s) at that institution,

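### Complications of research biopsies taken before the first erlotinib dose have no routine place in the safety data, and those of the compulsory mediastinal restaging are recorded but cannot be attributed to a study procedure.

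*Combined protocol and SAP*

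**What the plan says.** **Safety window.** Section 18.4 states: "All patients will be evaluated for toxicity from the time of their first treatment with erlotinib". In the 6.1 calendar, as the extracted table reads, the AE row is marked for the erlotinib visits (D1, 15, 29, 43), D57, post-surgical follow-up and the end-of-treatment visit. It is blank under Pre-study. Section 12.1 ties an AE to a subject who has been given a product and describes it as "temporally associated with the use of erlotinib whether or not considered related to erlotinib".

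**Pre-dose procedures.** On the correlative samples, 8.3.1 says: "Pre-treatment biopsy could be obtained within 2 weeks before initiation of the drug treatment". This covers tumour and skin. Tumour biopsies are planned in available patients, and skin biopsies in those who consent to them. Section 8.3.2 lists "CT-guided core biopsy of tumor" among the permitted sources.

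**Status of surgical procedures.** Section 18.4 continues: "All of the surgical procedures in the protocol are the usual standard of care in treating patients with stage III NSCLC". It then adds: "However, we will monitor and record all postoperative complications", and "Certain postoperative complications are expected after lung resection and/or mediastinoscopy".

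**Compulsory restaging.** Section 4.2 requires mediastinal restaging by EUS/EBUS or mediastinoscopy in patients without progression who do not go to surgery, and says: "Patients are also required to have repeat mediastinal evaluation even if the treating physician decides to continue on erlotinib beyond study duration".

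**The concern.** Safety is a secondary objective (1.2), and 18.1 puts all secondary analyses on an intent-to-treat basis. A window that opens at first dose suits the toxicity of erlotinib. It does not suit harm from procedures done for the correlative studies, some of which come before the drug. A consented patient who has a complication from a research biopsy, and perhaps never starts erlotinib because of it, would be in no toxicity count.

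The second strand is attribution. Section 4.2 makes restaging compulsory whatever the treating physician plans, and 18.1 allows mediastinoscopy as a source for the primary endpoint. It cannot be presumed usual care for every such patient. If its complications can be attributed only to drug or not to drug, the safety report cannot separate what the trial's own requirements caused from the background of resection and disease.

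**Working it through.** The plan gives no figure on this point, so the check sets the sections side by side.

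**1. Pre-dose research biopsy**

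| Rule | Does it reach a non-serious or expected biopsy complication before dosing? |
|---|---|
| 18.4 window | No; it opens at first dose |
| 6.1 AE row | No pre-study mark; the first check is at D1, so it reaches dosed patients only |
| 12.1 AE definition | No; the subject must have been given product |
| 12.1 CRF recording throughout the trial | Applies to AEs, so it inherits that definition |
| 12.1 Unanticipated Problem | Covers relation to study participation, but the event must also be unexpected and either serious or a sign of greater risk |
| 12.2 IRB reporting | Deaths within 30 days of a study-related procedure (sites under the Einstein IRB), and incidents showing more risk than was known |

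The serious or unexpected end is reached. Non-serious and expected complications are not, and neither is a never-dosed patient who has one.

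**2. Compulsory restaging**

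- *Timing.* It follows about two months of erlotinib (4.1, 4.2), so it falls inside the 18.4 window.
- *Recording.* Section 18.4 commits to recording all postoperative complications and names mediastinoscopy. Section 12.1 puts AEs on the CRF whether or not drug-related. The calendar has AE checks at D57 and end of treatment, and section 14 gives non-surgical patients the latter visit. These events are recorded.
- *Attribution.* Step 3 in 12.2 asks only about relation to protocol therapy. The Grade 2-3 rule in 12.5 asks about relation to the intervention and is introduced for erlotinib. Neither has a study-procedure category. Only the Unanticipated Problem test in 12.1 refers to study participation.
- *Conflict.* Section 18.4 calls all surgical procedures usual care, while 4.2 requires this one regardless of the care plan.

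**3. Scale, by assumption only**

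For n pre-dose biopsies with a common complication rate p and independent events, P(at least one) = 1 − (1 − p)^n.

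| n | p = 1% | p = 2% | p = 5% |
|---|---|---|---|
| 10 | 1 − 0.99^10 = 10% | 1 − 0.98^10 = 18% | 1 − 0.95^10 = 40% |
| 20 | 1 − 0.99^20 = 18% | 1 − 0.98^20 = 33% | 1 − 0.95^20 = 64% |

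Expected events n × p run from 10 × 0.01 = 0.1 to 20 × 0.05 = 1.0. Neither n nor p comes from the documents, and one rate is used for both skin punch and core biopsy.

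**The case against.** The best case against is that the plan already covers most of this, and much of that case stands.

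- **Restaging complications uncounted.** A reader might infer this from the usual-care sentence. The sentences that follow it in 18.4, the CRF rule in 12.1 and the D57 and end-of-treatment checks show otherwise. Some ambiguity is left: EUS/EBUS is not named in 18.4, and 4.1 takes patients who are not surgical candidates off study at about this time.
- **Monitoring committee blind to these events.** This too is not supported. Section 12.2 gives IRB routes, 12.3 logs non-reportable serious or unanticipated events for the committee, 12.4 provides monthly AE review, and the Grade 4 and 5 rules in 12.5 carry no relatedness condition within 30 days of last treatment.
- **Wrong benchmark in the suspension rule.** One might argue that the expected complication rate of compulsory restaging is zero. The rule most naturally concerns the three postoperative outcomes that 18.4 has just listed, and nothing says these patients would otherwise have gone without restaging.
- **The usual-care label settles attribution.** Section 12 does not say so. The label conflicts with 4.2 and may steer an assessor, but that is as far as it goes.
- **The pre-dose gap is small.** This partly stands. Diagnostic tissue is the main source, skin biopsy is optional, and a core biopsy may be the diagnostic one. A complication still present at D1 could be noted at that check. But no rule asks for it, and the D1 check does not reach a patient who is never dosed.

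Also fair: known biopsy complications would usually fail the unexpectedness test for expedited reporting, however they are attributed. The gain is in recording and tabulation more than in expedited reports.

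**Conclusion.** The point holds in two limited parts. First, under the plan's stated rules, non-serious or expected complications of pre-dose research biopsies have no routine place in the safety data, and a consented patient who is never dosed is outside it. Second, complications of the restaging required by 4.2 are recorded, but the expedited-reporting steps in 12.2 and the Grade 2-3 rule in 12.5 have no study-procedure attribution, and the blanket usual-care statement in 18.4 conflicts with 4.2.

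No magnitude can be stated beyond assumption. The illustration of a 10% to 64% chance of at least one unrecorded event rests on 10 to 20 biopsies and a 1% to 5% rate. Nor should a reader take half of the 55 patients, using the 50% resectability quoted in section 2.0 from the EORTC trial, as the number whose restaging harms are due to the trial. That figure comes from a chemotherapy trial, would include progressors whom 4.2 exempts, and assumes none would have been restaged anyway.

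No efficacy estimate or decision rule is affected. The case report form (Appendix E) is an attachment not included in the text, so whether it already has a suitable field cannot be checked.

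**What to change.** 1. **Window (18.4).** Keep all-cause toxicity from first dose. Add that, from consent or the first study-specific procedure, every event related to a study-specific procedure is recorded, including in patients never dosed. Section 8.0 already requires consent before correlative material is obtained, so consent is a workable start. Ask about such events at the existing D1 AE check, and by follow-up of patients who never start drug.
2. **Attribution (12.2, 12.5).** Add a *related to study procedure* category covering research biopsies and the restaging required by 4.2, whether by EUS/EBUS or mediastinoscopy.
3. **Usual-care sentence (18.4).** Limit it so that it no longer covers the restaging required by 4.2.

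The cost is a few sentences, possibly a CRF field, a slightly longer safety table and a few more recorded events. Dosed patients need no new visit, and no new procedure is needed. Patients never dosed need a follow-up contact.

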4.2.1 Mediastinoscopy

A mediastinoscopy is highly recommended for all patients prior to neoadjuvant therapy for confirmation of mediastinal disease and also for tissue acquisition for EGFR mutation testing.

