4.2.4 Operative complications

In hospital and 30 day morbidity and mortality will be prospectively monitored.

5.0 TOXICITIES, DOSE MODIFICATIONS, AND MANAGEMENT:

Adverse events should be coded according to CTCAE version 4 (Appendix C).³⁸

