12.4 Trial Monitoring

This trial will be monitored by the Albert Einstein Cancer Center Data Safety Monitoring Committee (AECC DSMC). A copy of the monitoring plan is maintained at the CPDMU. The DSMC as part of its function performs quarterly reviews of Clinical Trials Compliance Audits, monthly reviews Adverse Events Reports, and monthly reviews of internally monitored Phase I/Phase II trials for accrual and response. Other monitoring activities are established as necessary in a protocol specific manner.

This trial will be part of the monthly Quality Assurance Audits. Each patient will be evaluated within 8 weeks of registration. This permits evaluation of consent, eligibility, and treatment/dose modification/Adverse Event (AE) reporting, and data quality for the first cycle (or month) of treatment. Patients at participating sites are evaluated for eligibility and consent at the time of registration by clinical and administrative staff.

This trial may also be eligible for quarterly Quality Enhancement Audit. Each audit consists of a review of regulatory documents, pharmacy drug accountability (if applicable) and patient case review, confirming eligibility, protocol compliance and source documentation

The results of the audit will be presented at the following month's DSMC meeting. The DSMC has the authority to close trial to patient accrual should the risk to patients be excessive or results require a corrective plan from the Principal Investigator. All study suspensions and closures will be forwarded to the IRB and study sponsor. All audit reports are forwarded to the DSMC and presented to the DSMC by the Audit Committee Coordinator.

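### Does the suspension rule for surgical complications in section 18.4 need an expected rate and a statistical boundary?

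*Combined protocol and SAP*

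**What the plan says.** Section 18.4 names the events: "We will particularly monitor 30 day mortality, development of bronchopulmonary fistula or prolonged wound healing". It accepts a background level, "Certain postoperative complications are expected after lung resection and/or mediastinoscopy", and then sets the condition: "If the rate of these is more than what is expected as standard of care", the regulatory authorities are informed and "the trial will be suspended for toxicity". It follows toxicity from the first erlotinib dose.

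Other sections bear on how this is carried out:

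- Section 4.2.4: "In hospital and 30 day morbidity and mortality will be prospectively monitored".
- Section 12.4: the Data Safety Monitoring Committee (DSMC) reviews adverse event reports monthly and may close accrual if risk is excessive. "A copy of the monitoring plan is maintained at the CPDMU"; it is not among the documents reviewed.
- Section 17.0: a Data Safety Monitoring Board (DSMB) meets monthly, sees cumulative toxicity summaries, and considers whether the trial should continue, change or end.
- Sections 12.2 and 12.3: a death within 30 days of a study procedure or study drug goes to the IRB within 5 business days, even if anticipated.
- Section 12.5: fatal events on study, or within 30 days of the last intervention, need expedited reporting.

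**The concern.** The consequence in section 18.4 is worded as mandatory, but the condition cannot be computed from the protocol. No rate for the three events appears anywhere. The text does not say whether they are judged together or singly, who is counted, or how large an excess must be. Section 18.2, by contrast, prints counts, error rates and early-stopping probabilities for efficacy.

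The denominator could matter. Section 18.4 mentions mediastinoscopy as well as resection. Section 4.2.1 says "A mediastinoscopy is highly recommended for all patients prior to neoadjuvant therapy", and section 4.2 says "Patients with non-progressive disease who are not going for surgery should have mediastinal restaging done by either EUS/EBUS or mediastinoscopy". The count at risk might therefore be the resected patients or nearly everyone enrolled.

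If the sentence worked as an automatic rule, one early event could stop a trial with no excess risk, or the choice of denominator could decide the matter. The background (section 2.0) gives early surgical mortality as the reason an earlier surgical trial showed no overall survival benefit, so surgical risk matters here.

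**Working it through.** **The plan's own figures.** Section 18.4 has none to reproduce. The efficacy design in section 18.2 (stop at 3 or fewer of 19; negative at 12 or fewer of 55) does reproduce by exact binomial calculation. Early stopping is 0.684 at 15% and 0.133 at 30%, type I error 0.048 and power 0.801. None of this bears on toxicity.

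**Inputs.** The maximum of 55 patients comes from section 18.2. The number resected is not stated. I take 27, about half of 55, borrowing the 50% resectability that section 2.0 reports for a different regimen. Expected rates of 2%, 5% and 10% are assumptions. The three events are pooled.

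**Bare rule, 5% assumed.** Suspend when events/resections > 0.05, looking after each resection. One event exceeds 5% through resection 19 (1/19 = 5.3%; 1/20 = 5.0%, not above). From resection 20 to 27, two events are needed.

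- True rate 5%: 1 − 0.95^19 = 0.623. Add 0.95^19 × P(at least 2 events in 8) = 0.377 × 0.057 = 0.022. Total 0.644.
- True rate 10%: 1 − 0.90^19 = 0.865. Add 0.135 × 0.187 = 0.025. Total 0.890.

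With a single look at the end, two events of 27 are needed (2/27 = 7.4%), and the chance at a true 5% is 0.394. Over 10 to 55 resections and the three assumed rates, with a look after each, suspension at ordinary risk runs from 18% (2%, 10 resections) to 82% (10%, 55 resections).

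**What a boundary would change.** For comparison only, take the smallest count, at least two, whose exact binomial upper tail is at or below a fixed pointwise level. That level is chosen so that overall false suspension over 55 resections is at most 10% or 20%. An exact forward recursion on the event count, with a look after each of 27 resections, gives:

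| Assumed expected rate | Rule | Suspends at expected rate | At double | At triple |
|---|---|---|---|---|
| 2% | bare | 42.0% | 66.8% | 81.2% |
| 2% | boundary, 10% level | 6.2% | 20.1% | 36.4% |
| 5% | bare | 64.4% | 89.0% | 97.0% |
| 5% | boundary, 10% level | 7.4% | 32.6% | 61.8% |
| 5% | boundary, 20% level | 13.9% | 45.5% | 73.1% |
| 10% | bare | 74.8% | 97.0% | 99.8% |
| 10% | boundary, 10% level | 6.5% | 43.9% | 83.2% |

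At 5%, the 10%-level boundary misses a doubled rate in 100 − 32.6 = 67.4% of trials. The two-event minimum also means that a single death would not cross it.

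**Denominator.** Two events are 2/27 = 7.4% of resected patients but 2/55 = 3.6% of all enrolled, on either side of an assumed 5%. That contrast is the extreme case. The mediastinoscopies of section 4.2.1 come before erlotinib, and section 18.4 counts toxicity only from the first dose. What remains open is restaging mediastinoscopy in non-resected, non-progressing patients, for whom section 4.2 also allows EUS/EBUS.

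**Timing.** Sections 12.4 and 17.0 fix a monthly review, although neither is linked to the section 18.4 comparison. Section 18.2 expects 1–2 patients a month, so a monthly look comes close to a look after each resection.

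**The case for a change.** The strongest case for a change is that a sentence ordering suspension should let a reader see what triggers it, and this one does not. The wording is mandatory, while sections 12.4 and 17.0 give the committees discretion, so the protocol leaves open which governs. Monthly review does not soften the bare rule, because at this accrual it amounts to frequent looks. Naming a rate, a denominator and a pooling rule would take a few sentences, and citing the monitoring plan might be enough.

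Much of this stands. The rate, denominator, pooling rule and margin are absent, and the bare rule separates ordinary from excess risk poorly under every assumption tried. Two things limit its force. The high false-suspension figures depend on a mechanical reading that the text does not compel, and on rates that nobody has stated. The definitions are also not quite free: expected rates have to be sourced, and a protocol change needs IRB approval under section 15.2. A committee that reviews these events monthly, with each 30-day death already reported individually, can supply the comparison itself.

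**Conclusion.** No change to the plan is called for. Section 18.4 leaves out detail, but the detail belongs to a safety judgment that the protocol already gives to committees meeting monthly, with power to close accrual, supported by individual reporting of 30-day deaths. The monitoring plan held elsewhere may say more.

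Replacing the sentence with a statistical boundary would not be a clear improvement. At an assumed 5%, with pooled events and 27 resections, it would cut false suspension from 64% to 7% or 14%, and detection of a doubled rate from 89% to 33% or 46%. A sponsor may reasonably prefer a sensitive prompt for review in a surgical trial, and that choice is for the sponsor and the DSMC.

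These sizes rest on assumed rates, an assumed number resected and a literal reading of one sentence. The conclusion would weaken if section 18.4 were in fact run as an automatic trigger without committee review, which nothing in the documents shows.
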